8.2.1 Return and Retention of Study Drug/Device

The research pharmacist at NMH will assist with disposal of drugs.

8.1.2 We will use pill counts to document compliance with drugs.

9.0 CORRELATIVES/SPECIAL STUDIES

The goal of the planned laboratory correlative studies is to understand how changes in phosphate homeostasis affect endocrine regulators of bone and mineral metabolism and markers of bone turnover. Additional stored samples will be archived for future analyses of newly discovered biomarkers related to bone and mineral homeostasis and its regulation. Submission of samples for correlative studies is mandatory. The consent form will have a statement that will inform participants about the planned use of archived samples. Participants who chose not to have their samples archived may opt out.

9.1 Sample Collection Guidelines

We will collect blood (serum and plasma) and urine samples. Samples will be labeled with the subject's de-identified study number and collection date and delivered for storage to the team's freezers. Samples will be processed at the NUCATS CRU laboratory.

Samples will be collected at the intervals indicated in section 5.5.

9.2 Assay Methodology

Specialized assays include: **FGF23** ELISA (Immutopics, CA); **N terminal propeptide of Type 1 procollagen** (P1NP) ELISA (USCN Life Science, Houston, TX); and **C terminal cross-linked peptide** (CTX) ELISA (Immunodiagnostic Systems, Scottsdale, AZ). All measurements of specialized assays will be performed at specialized labs at Feinberg School of Medicine once the study has ended.

Standard assays (plasma and urinary calcium, phosphate and creatinine, LFTs, CBC, PTH) will be performed at NMH clinical labs.

9.3 Specimen Banking

Patient samples collected for this study will be retained in the study freezers located at CTMH at [name] and/or in the Freezer Farm at the Tarry Research Building at [name]. Specimens will be stored indefinitely or until they are used up. If future use is denied or withdrawn by the patient, best efforts will be made to stop any additional studies and to destroy the specimens.

[name] will be responsible for reviewing and approving requests for clinical specimen from potential research collaborators outside of NU.

Collaborators will be required to complete an agreement (a Material Transfer Agreement or recharge agreement) that states specimens will only be released for use in disclosed research. Any data obtained from the use of clinical specimen will be the property of NU for publication and any licensing agreement will be strictly adhered to.

The specimens, DNA, and their derivatives may have significant therapeutic or commercial value. The Informed Consent form contains this information and informs the subject that there is the potential for financial gain by NU, the investigator or a collaborating researcher or entity.

The following information obtained from the subject's medical record may be provided to research collaborators when specimens are made available:

- Collection time in relation to study treatment
- Demographic data
- De-identified stored samples

10.0 STATISTICAL CONSIDERATIONS

10.1 Study Design/Study Endpoints

This is a 2-week, randomized, double-blinded, 2x2 factorial design study of 80 healthy volunteers (20 in each of the four treatment groups) investigating the effects of the

interventions on changes in plasma and urinary phosphate. Participants will be randomized to one of the four groups: 1) lanthanum carbonate + nicotinamide; 2) lanthanum carbonate + nicotinamide placebo; 3) lanthanum carbonate placebo + nicotinamide; 4) lanthanum carbonate placebo + nicotinamide placebo.

The end-points are listed in the table below:

Summary of End Points			
End-Point	Primary	Secondary	Justification
Plasma Phosphate	X		Marker of phosphate handling
24-hr Urine Phosphate	X		Marker of phosphate handling
FePI	X		Marker of phosphate handling
PTH		X	Hormonal regulator of mineral metabolism
FGF23		X	Hormonal regulator of mineral metabolism
P1NP		X	Bone formation marker
CTX		X	Bone resorption marker

10.2 Sample Size and Accrual

Assumptions based on prior studies:

- Data on effects of nicotinamide on blood or urine phosphate in healthy volunteers are not available.
- Similarly, data on the combined use of the nicotinamide and lanthanum carbonate are lacking.
- Therefore, we relied on published data of the effects on lanthanum carbonate on 24-hour urine phosphate. In previous short-term studies of healthy volunteers, lanthanum carbonate at the dose that we will use in our study decreased 24-hour urine phosphate by 236 to 468 mg/day.²⁹ The within group standard deviation of change in 24-hour urine phosphate ranged from 168 to 294 mg/day.²⁹

Derivation of the sample size for this study:

Using the PS Power and Sample Size calculator (independent t test), we estimated that a sample size of 20 participants per group will yield 80% power to detect a difference of 273 mg/dl in urine phosphate, at $\alpha=0.05$, assuming a within group SD of the change in 24-hour urine phosphate of 300 mg/day. Assuming a conservative within group SD of the change in plasma phosphate of 0.55 mg/dl, the sample size of 20 volunteers per group will allow us to detect a difference as small as 0.50 mg/dl in plasma phosphate.

Importantly, we based our power calculations on t-tests that compare pre to post intervention changes across two groups. Because the repeated measures analyses we will employ using linear mixed models will reduce within-subject variability, we expect to have more power than is tabulated above and view the presented power calculations as conservative estimates. Additionally, power for main effects analyses (effects of lanthanum carbonate alone and nicotinamide alone; 40 participants per groups; margin comparison) will be greater than the presented power for comparisons of dual treatment to placebo (20 participants per group; individual cell comparison).

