1.0 BACKGROUND AND RATIONALE

1.1 Disease Background

Chronic kidney disease (CKD) is a growing public health problem that increases risks of end-stage renal disease (ESRD), cardiovascular disease (CVD), fractures, and death, and it poses an enormous financial burden on the US health system.¹⁻³ Existing therapies modestly impact outcomes.⁴⁻⁸ Novel strategies targeting CKD-specific mechanisms are urgently needed to improve health and reduce cost.

CKD is complicated by disordered mineral metabolism, characterized by abnormal calcium and phosphate homeostasis, calcitriol and klotho deficiency, and elevated levels of parathyroid hormone (PTH) and fibroblast growth factor 23 (FGF23).⁹ Elevated FGF23 is the earliest and most common manifestation of disordered mineral metabolism.¹⁰ Observational studies report independent associations between elevated phosphate and FGF23 blood levels and increased risks of ESRD, CVD and death.¹¹⁻¹³ As potential explanatory mechanisms, phosphate excess induces arterial stiffness due to vascular calcification, and FGF23 excess contributes directly to the pathogenesis of left ventricular hypertrophy (LVH).^{14,15} Together, these effects promote CVD events and death.¹²

Dietary phosphate absorption is a modifiable determinant of phosphate and FGF23 levels.¹⁶⁻¹⁸ Small studies of short duration suggest that phosphate binders and dietary phosphate modification in CKD can lower phosphate and FGF23 blood levels by reducing paracellular absorption of phosphate in the gut.¹⁹ However, animal studies demonstrate that compensatory upregulation of transcellular phosphate absorption via the sodium phosphate co-transporter, NPT2b, reduces the efficacy of these approaches.^{20,21} Since nicotinamide lowers plasma phosphate by reducing gut expression of NPT2b,²² we hypothesize that use of nicotinamide combined with phosphate binders on a background of dietary phosphate moderation will most effectively reduce phosphate and FGF23 blood levels in CKD. We plan to advance this approach in future randomized clinical trials.

The objective of this study is to perform a detailed physiologic study of healthy volunteers to assess the short-term effects of nicotinamide alone, lanthanum carbonate alone, or both in combination, on phosphate homeostasis. The results from healthy volunteers will provide information needed for optimal design of studies for patients with CKD.

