2.0 STUDY OBJECTIVES

2.1 Primary Objectives

2.1.1 To determine the short-term effects of lanthanum carbonate and nicotinamide, alone and in combination, on phosphate handling, as measured by plasma phosphate, 24-hour urinary phosphate and fractional excretion of phosphate in healthy volunteers

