10.3 Data Analyses Plans

- We will study changes over time in absolute levels of the primary and secondary end-points.
- We will use mixed-model, repeated-measures analyses to assess the changes.
- Model terms will include:
 - fixed-effects treatment terms (treatment group);
 - the interaction between each treatment and time (nicotinamide x time and lanthanum carbonate x time);
 - the interaction between treatments (nicotinamide x lanthanum carbonate);
 - the interaction between treatments and time (nicotinamide x lanthanum carbonate x time);
 - random-effects terms, connoting individual participants.
- If the interaction term between treatments and time (nicotinamide x lanthanum carbonate x time) is significant, we will compare the response in the dual intervention group to the placebo group.
- If the interaction term between treatments and time (nicotinamide x lanthanum carbonate x time) is not significant, we will examine the main effects of each intervention.
- We will use natural log transformation for end points with skewed distribution.
- If there are significant differences ($p<0.05$) in age, gender and baseline eGFR across randomized treatment groups, we will adjust for these covariates.
- Standard descriptive analyses will be used for safety evaluations.

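### Section 10.2 calls the 40-per-group margins each drug's effect alone; that holds only without interaction, and 10.3 names no monotherapy v double-placebo contrast

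*Combined protocol and SAP*

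**What the plan says.** The primary objective in section 2.1 is "To determine the short-term effects of lanthanum carbonate and nicotinamide, alone and in combination, on phosphate handling"; section 2.2 asks the same of the secondary end points. Section 10.1 describes a "2x2 factorial design study of 80 healthy volunteers (20 in each of the four treatment groups", with the arms "1) lanthanum carbonate + nicotinamide; 2) lanthanum carbonate + nicotinamide placebo; 3) lanthanum carbonate placebo + nicotinamide; 4) lanthanum carbonate placebo + nicotinamide placebo".

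Section 10.2 sizes the trial on a two-group t test: "a sample size of 20 participants per group will yield 80% power to detect a difference of 273 mg/dl in urine phosphate", "assuming a within group SD of the change in 24-hour urine phosphate of 300 mg/day". (The difference is printed in mg/dl. I read it as mg/day, the unit of its SD.) For plasma phosphate it gives 0.50 mg/dl at an SD of 0.55. It then says that power for the main effects exceeds that of dual treatment v placebo, and glosses the main effects as "effects of lanthanum carbonate alone and nicotinamide alone; 40 participants per groups; margin comparison".

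Section 10.3 fits a repeated-measures mixed model with both drug-by-time terms, the drug-by-drug term and the three-way term. If the three-way term is significant, the one comparison named is dual treatment v placebo. If it "is not significant, we will examine the main effects of each intervention". Neither branch names monotherapy v double placebo.

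**The concern.** From the arm list, the 40 people in the lanthanum margin are 20 on both drugs and 20 on lanthanum with nicotinamide placebo. Their 40 comparators are 20 on nicotinamide and 20 on double placebo. The nicotinamide margin has the same structure. Each margin thus averages the drug's effect with and without the other drug. That is a legitimate quantity, but it is the effect of the drug alone only when the two drugs do not interact, and 10.2 does not state that condition.

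The trial's own rationale makes interaction plausible. Section 1.1 reports from animal work that "compensatory upregulation of transcellular phosphate absorption via the sodium phosphate co-transporter, NPT2b, reduces the efficacy of these approaches", the approaches being binders and dietary modification, and proposes nicotinamide because it reduces NPT2b expression. Section 10.2 says that data on the combination are lacking.

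At stake is part of the primary objective. If the three-way term is significant, the alone effects differ from the margins and the plan names no estimate of them. If it is not, the margins are reported, and 10.2 invites the reader to take them as alone effects.

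**Working it through.** **Inputs.** Four cells of 20 (10.1). SD of change 300 mg/day for urine and 0.55 mg/dl for plasma, alpha 0.05 (10.2). I take the tests as two-sided because that reproduces the plan's figures. Like 10.2, the checks use a single change score and ignore repeated measures, dropout and multiplicity.

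**1. What the margin estimates.** Write the mean changes as m11 (both drugs), m10 (lanthanum only), m01 (nicotinamide only) and m00 (double placebo).

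- Lanthanum alone: A = m10 − m00.
- Interaction: I = m11 − m10 − m01 + m00.
- Lanthanum margin: (m11 + m10)/2 − (m01 + m00)/2 = [A + (A + I)]/2 = A + I/2.

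The same holds for nicotinamide.

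**2. The plan's own figures (20 v 20, 38 df, noncentral t).**

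- Urine: SE = 300 × √(2/20) = 94.9; 273/94.9 = 2.88; power 80.1%.
- Plasma: SE = 0.55 × √(2/20) = 0.174; 0.50/0.174 = 2.87; power 80.0%.

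Both reproduce.

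**3. Alone effect.** Monotherapy v double placebo is also 20 v 20, so its SE is again 94.9 and its power at 273 mg/day is the same 80.1% (81.1% if the SD is pooled over four cells, 76 df). It is not greater than that of dual v placebo.

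**4. Margin (40 v 40).**

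- Urine: SE = 300 × √(2/40) = 67.1; 80% power at 190 mg/day; 98.0% at 273.
- Plasma: SE = 0.55 × √(2/40) = 0.123; 80% power at 0.35 mg/dl.
- Ratio of SEs: 94.9/67.1 = 1.41.

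**5. The gate.** SE of the interaction = 300 × √(4/20) = 134.2, 76 df. Power is 80% at an interaction of 381 mg/day, but 7%, 11%, 20% and 31% at 50, 100, 150 and 200.

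**6. Size if a margin is read as an alone effect.** The documents give no interaction size, so these are assumed values. Suppose nicotinamide alone has no effect on 24-hour urine phosphate but adds a further reduction on top of lanthanum. I simulated the two-stage rule with 400,000 trials per row, SD 300 and 76 df.

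| Assumed interaction (mg/day) | Gate non-significant | True nicotinamide margin (mg/day) | Gate non-significant and margin significant, % of all trials |
|---|---|---|---|
| 50 | 93% | 25 | 6% |
| 100 | 89% | 50 | 10% |
| 150 | 80% | 75 | 16% |
| 200 | 69% | 100 | 21% |

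At 200, the margin is significant in 31% of the trials that pass the gate as non-significant, so its 95% CI covers the true alone effect of zero in 69% of them.

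**7. The other direction.** Suppose a drug alone gives 273 mg/day and the combination loses 25%, 50% or 100% of that amount. The margin is then 239, 205 or 137 mg/day, with power 94.0%, 85.4% or 52.0%; the gate's power is 7.9%, 17.1% or 52.0%. Margin power falls below the 80% cell power once the loss exceeds about 60%.

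**The case against.** Much of the case for the plan stands.

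- A reader might infer that the higher power in 10.2 does not exist. The documents do not support that. The sentence is about main effects as a margin comparison, and for that quantity it is right: 98.0% against 80.1% at the same difference. Under additivity the margin equals the alone effect and estimates it more precisely, which is the usual reason for a factorial design.
- A reader might infer that the alone effects receive no analysis at all. That also goes too far. The non-significant branch estimates them if the drugs are additive, and the 10.3 model contains the terms from which the cell contrasts can be derived. What is missing is their pre-specification.
- A reader might infer that the main effect is undefined because its coefficient depends on how treatment is coded. Section 10.2 settles this by calling it a margin comparison.
- Section 10.3 itself speaks of main effects and does not use the word alone. In the examples above the margin is truly non-zero, so rejecting its null is correct; the claim is false only if the result is then presented as an alone effect.
- The larger assumed interactions are at the unfavourable end. Section 1.1 hypothesises that the combination works best, which additivity also satisfies, and its evidence of compensation comes from animals.
- The 20-per-group calculation in 10.2 already serves any pair of cells, including monotherapy v placebo.

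None of this supplies the missing condition in 10.2 or the missing contrasts in 10.3. A non-significant gate is also not good evidence of additivity when it has 31% power at 200 mg/day.

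**Conclusion.** The point holds as a labelling error in 10.2 and an omission in 10.3. The margins are average effects over the other drug, and their advantage (80% power at 190 rather than 273 mg/day) belongs to the alone effects only without interaction. The gate cannot secure that condition, since it has 80% power only at about 381 mg/day. When the gate is significant, the plan names no estimate of the alone effects, which is when they are most needed.

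The detectable differences rest on the plan's own SDs, two-sided t tests and full follow-up. The 6% to 21% rates are illustrative: they assume no effect of nicotinamide alone, interactions of 50 to 200 mg/day, and a margin reported as an alone effect. The correction is worth making because it lets the trial answer its stated primary objective, but the sample size and design are not in question. Severity: should fix.

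**What to change.** **Section 10.3.** For every primary and secondary end point, and whatever the interaction p value, pre-specify two contrasts from the planned model, each with a 95% CI: lanthanum + nicotinamide placebo minus double placebo, and nicotinamide + lanthanum placebo minus double placebo. Call the margins average effects over the other drug. State whether the new contrasts are formal tests or estimates, since they add two per end point.

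**Section 10.2.** Replace the parenthesis with:

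- alone effects, 20 v 20: 80% power at 273 mg/day and 0.50 mg/dl, the same as dual v placebo;
- average effects (margins), 40 v 40: 80% power at 190 mg/day and 0.35 mg/dl, interpretable as alone effects only without interaction.

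**Cost.** Analysis wording only, with no added participants, visits or assays. The alone effects carry CIs about 1.41 times wider than the margins, so the stated power for them looks less favourable, and there are 14 more estimates over the seven end points.

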10.3 Data Analyses Plans

- We will study changes over time in absolute levels of the primary and secondary end-points.
- We will use mixed-model, repeated-measures analyses to assess the changes.
- Model terms will include:
 - fixed-effects treatment terms (treatment group);
 - the interaction between each treatment and time (nicotinamide x time and lanthanum carbonate x time);
 - the interaction between treatments (nicotinamide x lanthanum carbonate);
 - the interaction between treatments and time (nicotinamide x lanthanum carbonate x time);
 - random-effects terms, connoting individual participants.
- If the interaction term between treatments and time (nicotinamide x lanthanum carbonate x time) is significant, we will compare the response in the dual intervention group to the placebo group.
- If the interaction term between treatments and time (nicotinamide x lanthanum carbonate x time) is not significant, we will examine the main effects of each intervention.
- We will use natural log transformation for end points with skewed distribution.
- If there are significant differences ($p<0.05$) in age, gender and baseline eGFR across randomized treatment groups, we will adjust for these covariates.
- Standard descriptive analyses will be used for safety evaluations.

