1.4 Rationale

The justification for the combined approach of binders with nicotinamide to modify plasma phosphate and FGF23 levels in CKD is rooted in our current understanding of the underlying biology. However, detailed human physiologic studies investigating the joint effects of these agents on blood and urine levels of mineral metabolites are not available in health or in CKD. Animal data consistently demonstrate that nicotinamide blocks small bowel Pi absorption by decreasing protein levels of NaPi2b.^{20,21} Some studies also suggest that nicotinamide may block phosphate reabsorption at the renal proximal tubule,³⁰ but this has not been studied in detail in healthy volunteers or CKD patients. Finally, the effects of nicotinamide on FGF23, PTH, calcitriol, and other parameters of mineral metabolism are unexplored in humans. Therefore, our proposed study will fill critical gaps that are needed to advance this novel therapeutic approach into future clinical trials.

We propose to study healthy volunteers because detailed data on the effects on mineral metabolism of nicotinamide alone or in combination with binders in this population are not available. In the future, we will also extend the proposed studies to patients with CKD.

Given that 24-hr urinary phosphate excretion declines and fractional phosphate excretion rises with progressive CKD, an additional justification for the study of healthy volunteers is the ability to easily detect changes following proposed interventions in both 24-hour and fractional urinary phosphate excretion.

For this detailed physiologic study, we chose to use the 2x2 factorial study design because we are specifically interested in investigating the effects of the combined interventions as compared to the effects of the placebo and to each monotherapy group.

We chose plasma phosphate, 24-hour urine phosphate, fractional urinary excretion of phosphate (FePI), FGF23 and PTH as end-points because we are interested in the effects of the interventions on phosphate handling and mineral metabolism (See Table). Additional end-points will include markers of bone turnover, including N terminal propeptide of Type 1 procollagen (P1NP) and C terminal cross-linked peptide (CTX) to assess the influence of the interventions on bone metabolism.

Summary of End Points			
End-Point	Primary	Secondary	Justification
Plasma Phosphate	X		Marker of phosphate handling
24-hr Urine Phosphate	X		Marker of phosphate handling

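### Section 10.3 names no combination-versus-monotherapy contrast and allows the powered combination-versus-placebo contrast only after a significant interaction test of unstated power

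*Combined protocol and SAP*

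**What the plan says.** Section 1.4 gives the reason for the factorial design: an interest in "investigating the effects of the combined interventions as compared to the effects of the placebo and to each monotherapy group". Objective 2.1.1 makes the effects of the two drugs, "alone and in combination, on phosphate handling", primary.

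Section 10.2 states that a "sample size of 20 participants per group will yield 80% power to detect a difference of 273 mg/dl in urine phosphate", at an SD of 300 mg/day. It identifies this as the "presented power for comparisons of dual treatment to placebo (20 participants per group; individual cell comparison", and says that power for the main effects ("effects of lanthanum carbonate alone and nicotinamide alone; 40 participants per groups; margin comparison") will be greater. It gives no power for an interaction and does not mention power for combination versus monotherapy.

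Section 10.3 branches on the nicotinamide x lanthanum x time term. If the term "is significant, we will compare the response in the dual intervention group to the placebo group". If it "is not significant, we will examine the main effects of each intervention". No other treatment contrast is named, and no significance level is set for the branching test.

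**The concern.** Three gaps appear when 10.3 is read against 1.4, 2.1.1 and 10.2.

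1. No direct contrast of the combination with lanthanum alone or nicotinamide alone is named in either branch, although that comparison is a stated reason for the design.
2. The comparison the trial is sized for is planned only after a significant interaction, and nobody has stated how likely that is.
3. When the interaction is significant, no monotherapy effect is named, although effects of each drug alone are primary. When it is not significant, the margins address combination versus monotherapy only under additivity, and a non-significant test does not show additivity.

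At stake is whether the headline comparison is made at all, and whether a margin is read as the gain from adding the second drug when it may not be. If the missing contrasts are specified only after unblinding, their form and order will have been chosen with the data in view.

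**Working it through.** **Inputs.** From 10.1 and 10.2: 20 per cell; SD of change in 24-hour urine phosphate 300 mg/day (plan), published range 168 to 294; plasma phosphate SD 0.55 mg/dl; alpha 0.05, taken as two-sided because that reproduces the plan's figure. Section 10.2 prints the 273 in mg/dl; it is read here as mg/day to match its SD. Assumed: the interaction sizes, a two-sided 0.05 gate, equal SDs, no dropout, and a single pre-to-post change per participant in place of the three-way time term. The mixed-model test could have more or less power.

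**Plan's figure.** Cell contrast: SE = 300 x sqrt(2/20) = 94.9, 38 df. Noncentral t power at 273 is 80.1%. For plasma, 0.50 mg/dl at SD 0.55 gives 80.0%. Both reproduce.

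**Interaction test.** Write D, L, N, P for the mean changes under dual, lanthanum, nicotinamide and placebo, with reductions positive, and I = D - L - N + P. Then SE(I) = SD x sqrt(4/20), 76 df: 134.2 at SD 300 and 75.1 at SD 168.

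| | SD 300 | SD 294 | SD 168 |
|---|---|---|---|
| Power at I = 136.5 | 17% | 18% | 43% |
| Power at I = 273 | 52% | 54% | 95% |
| I detectable with 80% power | 381 | 373 | 213 |

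Plasma: SE = 0.55 x sqrt(0.2) = 0.246; power is 52% at 0.50 mg/dl, and 80% needs 0.70.

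**The gated contrast.** D - P and I are orthogonal (coefficients on D, L, N, P are 1, 0, 0, -1 and 1, -1, -1, 1; their product sums to zero). The chance that dual versus placebo is both run and significant is therefore close to the product of the two powers. At SD 300, with pooled variance, the ungated contrast has 81.1% power at 273. Under additivity the product is 0.05 x 0.811 = 4.1%. If the whole effect is interaction it is 0.520 x 0.811 = 42%. Simulation of the four cell means (1,000,000 sets per scenario, P = 0, D = 273) gives:

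| Scenario | I | Run and significant, SD 300 / 294 / 168 |
|---|---|---|
| L = N = 136.5 | 0 | 4% / 4% / 5% |
| L = 236, N = 37 | 0 | 4% / 4% / 5% |
| L = N = 68.25 | 136.5 | 14% / 15% / 43% |
| L = N = 236 | -199 | 25% / 27% / 74% |
| L = N = 0 | 273 | 42% / 45% / 95% |

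Ungated, it is significant in about 80% / 82% / over 99% (38 df). Under additivity the gate opens in 5% of trials whatever the SD or sample size, so the extra precision 10.2 expects from repeated measures cannot help there.

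**What the margins estimate.** The nicotinamide margin is [(D - L) + (N - P)]/2 = (N - P) + I/2 = (D - L) - I/2. It equals both the effect alone and the increment over lanthanum only if I = 0. Take L = N = 236, the low end of the lanthanum range in 10.2 ("decreased 24-hour urine phosphate by 236 to 468 mg/day"), assumed for nicotinamide too, with D = 273. The true increment over either drug is 273 - 236 = 37. I = 273 - 236 - 236 = -199, so each margin estimates 236 - 99.5 = 136.5. The gate stays shut in 69% / 68% / 26% of such trials. It is shut while a given margin is significant in about 35% / 36% / 24%.

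**The case against.** - **The rule excludes nothing.** Section 10.3 says what will be done in each branch and does not forbid other contrasts, and the model can supply them all. True, but a pre-specified plan is judged by what it names, and the natural reading is conditional.
- **Effects alone may be covered.** If the factors are reference-coded, the drug-by-time coefficients are each drug versus placebo; and 10.2 itself calls the margins effects of each drug alone. Coding is not stated, and the margin is the effect alone only under additivity. The usage in 10.2 does soften the third gap where the interaction is not significant.
- **Section 1.4 already names the comparisons.** This stands in part: the question is pre-stated. What is missing is its test and its place in the testing order.
- **The trial would seldom come away empty.** This stands. At SD 300 some planned result is significant in 77% (equal split) to 93% (236 + 37) of additive trials, and in 77% to 79% of the non-additive scenarios. At SD 168 it exceeds 99% throughout. Under additivity the margins are the more precise analysis. The rule mainly changes which claim is made; a significant margin is not a test of dual versus placebo.
- **The scenarios are chosen.** All fix the combination effect at 273, a detectable rather than an expected difference, and section 10.2 says there are no nicotinamide data in healthy volunteers. The percentages are therefore illustrative. The mismatch between sections needs none of them.

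**Conclusion.** The concern holds. Section 10.3 does not carry through the comparisons that sections 1.4 and 10.2 set up: combination versus each monotherapy is never directly tested, and combination versus placebo is tested only through a gate of unstated power. For a true combination effect of 273 mg/day at SD 300, the chance of a significant planned test of that contrast falls from about 80% to between 4% (additive) and 42% (all interaction). At SD 168 it falls from over 99% to between 5% and 95%. These figures rest on assumed interaction sizes and a change-score stand-in for the three-way term. Section 1.1 gives only background support for non-additivity: its transporter evidence is from animals and its hypothesis concerns CKD. The data remain usable, so this should be fixed in the plan; it does not undermine the design.

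**What to change.** Replace the two conditional bullets in 10.3.

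- Whatever the interaction p-value, estimate from the same fitted model, with 95% confidence intervals, dual versus placebo, dual versus lanthanum, dual versus nicotinamide, and each monotherapy versus placebo, for the pre-to-post change that 10.2 sizes.
- Report the interaction as an estimate with its interval, not as a gate.
- Keep the margins as planned analyses, stating that they equal the effects alone, and dual minus the other drug, only under additivity.
- State the testing order, including the monotherapy effects that 2.1.1 makes primary. The order is the sponsor's choice.
- State the power of the dual-versus-monotherapy contrasts. The 20-versus-20 calculation in 10.2 carries over: 273 mg/day is detectable at SD 300.

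The cost is wording; data and model are unchanged. The price is precision. A cell contrast detects 273 mg/day with 80% power against 190 for a margin at SD 300 (SE = 300 x sqrt(1/20) = 67.1), and 153 against 107 at SD 168. Under additivity, an increment of 136.5 has 29% power as a cell contrast and 52% as a margin at SD 300 (71% and 95% at SD 168). The dual-versus-monotherapy contrasts may be inconclusive and should be read mainly as estimates.
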